## **8.10 Day 90**

For all patients:

- On Day 90 ( $\pm 7$  days), conduct a mortality assessment (may be completed by phone call to patient, LAR, primary MD, or chart review)

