For all 4 cohorts, a study physician or appropriately trained delegate will perform all assessments daily through Day 10, or until discharge if occurring earlier. After Day 10, and starting on Day 12, serious adverse events (SAEs) will be captured every 48 hours until Day 30 ( $\pm$  2 days), or until discharge if occurring earlier. Patients discharged prior to Day 30 will be contacted on Day 30 ( $\pm$  2 days) to capture SAEs and any re-admissions to the hospital. Patients will also be contacted on Day 90 ( $\pm$  7 days) to assess mortality.

CalciMedica may submit amendments to the protocol to modify the planned doses, the dosing schedule, the infusion time, the number of sites in the study, the total number of patients randomized in the study, the number of patients randomized in each cohort, the number of cohorts in each phase of the study, and/or the number of phases in the study for safety and/or efficacy considerations.

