## 9.7 Reporting of Serious Adverse Events

The Investigator is responsible for reporting to CalciMedica or designee within 24 hours from the time when site personnel learn about the event all SAEs that are observed or reported by the patient during the study (from randomization until the patient dies, the patient withdraws consent, or the patient's participation in the study ends) regardless of the relationship to CM4620-IE or clinical significance. Any additional information that becomes available later should be submitted within 1 working day of receipt. All SAEs reported or observed during the study must be followed to resolution or until the Investigator deems the event to be chronic or the patient to be stable. CalciMedica or its designee may contact the Investigator to obtain additional information on any SAE that has not resolved at the time the patient completes the study. SAEs ongoing at database lock will be noted as such.

CalciMedica or its designee will notify the regulatory authority of any fatal or life threatening unexpected related events associated with the use of CM4620-IE as soon as possible but no later than seven calendar days after the initial receipt of the information. Initial notification will be followed by a written report within fifteen calendar days. For SAEs that do not meet the fatal or life threatening unexpected related criteria, CalciMedica or its designee will notify the appropriate regulatory agencies in writing within fifteen calendar days.

CalciMedica or its designee will provide copies of any reports to regulatory agencies regarding unexpected SAEs to the Investigators for review and submission to the institutional review board (IRB), Ethics Committee (EC) or Research Ethics Board (REB). The PIs are responsible for informing their IRB, EC, or REB of any SAEs at their site. SAE correspondence with regulatory authorities, IRBs, ECs or REBS must be submitted to CalciMedica or its designee for filing.

In addition, the following adverse events that are commonly observed in this patient population will not be reported to the regulatory authority as individual expedited reports except in unusual circumstances:

- Hypoxemia and acute respiratory distress syndrome
- Oliguria and acute kidney injury
- Hypotension and shock
- Bacteremia
- Pneumonia
- Obtundation
- Splanchnic venous thrombosis
- Abdominal compartment syndrome
- Gastroparesis and ileus
- Local complications of the pancreas and peripancreatic tissue

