## Appendix 11 Schedule of Events

	Screen	Day 1	Day 2	Day 3	Day 4	Day 5	Days 6,7	Days 8,9	Day10 h	Days 12-28 a	Day 30 b	Day 90 c
Informed Consent	X											
Demographics & Medical History	X											
Concomitant Medications		X	X	X	X	X	X	X	X			
Physical Examination (limited)	X								X			
Vital Signs e	X	X	X	X	X	X	X	X	X			
Height and Weight	X											
Serum Pregnancy Test for WOCBP	X											
Blood sample for amylase or lipase d	X											
Determine Presence of SIRS d	X											
Blood Sample for Serum Chemistries		X	X	X	X	X	X	X	X			
Blood Sample for CBC, Diff & Platelets e	X	X	X	X	X	X	X	X	X			
Blood and Urine Sample for Biomarkers		X	X	X	X	X	X	X	X			
Blood Sample for PK Analysis f		X	X		X	X			X			
Arterial Blood Gas g		X				X			X			
SpO 2 by Pulse Oximetry and FiO 2	X	X	X	X	X	X	X	X	X			
Calculate Glasgow Coma Scale Score		X	X	X	X	X	X	X	X			
CECT of the Pancreas	X					X (Day 5 to Day 7)						
Assess Pain		X	X	X	X	X	X	X	X			
Randomize patient i		X										
AE/SAE Evaluation		X	X	X	X	X	X	X	X	X	X	X
CM4620-IE Administration		X	X	X	X							

a Safety and tolerability assessments after Day 10 will be done every 48 hours until Day 30 or until discharge, whichever occurs first

b Day 30 visit ( $\pm$  2 days): for patients who have been discharged prior to Day 30, the visit will consist of a telephone call to the patient, the LAR, or the primary MD, or chart a review for an SAE evaluation and to determine if patient has had a readmission to the hospital.

c Day 90 ( $\pm$  7 days) visit will consist of a telephone call to the patient, the LAR, or the primary MD, or chart a review for mortality.

d Blood samples for amylase or lipase and CBC, Diff and platelets at screening will be analyzed at local lab. SIRS will determined using local labs at screening

e Vital signs and CBC, differential and platelets drawn every 12 hours on Days 1-5.

f A PK sample will be obtained 30 minutes ( $\pm$  15 min) after and 8 hours ( $\pm$  30 min) after completion of CM4620-IE administration on Day 1 and Day 4. A PK sample will be obtained 30 minutes prior to administration of CM4620-IE on Day 2. On Day 5, and on Day 10, or discharge if earlier, a PK sample will be obtained.

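### Day 90 is a mortality-only contact in the text but is ticked for AE/SAE evaluation in the schedule, so non-fatal SAEs between Day 30 and Day 90 may be ascertained inconsistently

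*Protocol*

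**What the plan says.** **Day 90 as a mortality contact.** Section 8.10 of the protocol has sites "conduct a mortality assessment" at Day 90 (±7 days), by telephone or from the chart, and lists nothing else. Section 3.1 says "Patients will also be contacted on Day 90" and gives mortality as the only purpose; the synopsis and SAP section 3.2 say the same. In Appendix 11, footnote c states that the Day 90 "visit will consist of a telephone call to the patient, the LAR, or the primary MD, or chart a review for mortality".

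**Where scheduled SAE questioning stops.** Under section 3.1, patients discharged before Day 30 are contacted at Day 30 (±2 days) "to capture SAEs and any re-admissions to the hospital". Section 8.9 has inpatients assessed every 48 hours until discharge or Day 30. Footnote a of the schedule ends post-Day 10 safety assessments at the same point.

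**Day 90 as a safety contact.** The "AE/SAE Evaluation" row of the same schedule is ticked at Day 90. Section 9.7 requires prompt reporting of "all SAEs that are observed or reported by the patient during the study", from randomization until death, withdrawal of consent or the end of participation. Section 9.4 sets the same end for recording AEs. Section 3.2 defines the end of the study by the last patient's Day 90 visit.

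**The SAP.** Section 3.1.2 makes adverse events a primary endpoint. Section 7.1.2 calls for frequency tables on a TESS approach and gives no closing day.

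**The concern.** The two readings ask different things of a site. Section 9.3 requires a standard non-directed question to the patient at every AE/SAE assessment. If the Day 90 tick governs, that question is due at Day 90. If section 8.10 and footnote c govern, a chart check of vital status is enough.

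Section 9.7 does not close the gap. It covers events that are seen or volunteered, and a discharged patient whom nobody asks may volunteer nothing. Readmission is specifically asked about only at Day 30, although hospitalization is an SAE criterion in section 9.2.

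The window is not clinically empty by the protocol's own account. The guideline summary in Appendix 7 places some interventions for necrosis at 4 weeks or more, and cholecystectomy for persisting collections beyond 6 weeks. Section 1.6 adds that prolonged residual drug levels were the reason a third multiple-dose group of healthy subjects was not dosed. At stake is whether the SAE tables, which serve the primary objective, rest on one defined follow-up period.

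**Working it through.** The plan gives no figure on this point to reproduce. The check compares the texts and does day arithmetic.

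**1. Is Day 90 really ticked?** The schedule has 12 columns: Screening, Days 1, 2, 3, 4, 5, 6–7, 8–9, 10, 12–28, 30 and 90. That leaves 12 − 1 = 11 after Screening. The AE/SAE row has a blank Screening cell and 11 ticks, so Day 90 is ticked.

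**2. What each place says about SAEs after Day 30**

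| Place | After Day 30 |
|---|---|
| Protocol synopsis, 3.1, 8.10; SAP 3.2 | Mortality contact only |
| Appendix 11, footnote a | Scheduled safety assessments end at Day 30 or discharge |
| Appendix 11, footnote c | Day 90 is for mortality |
| Appendix 11, AE/SAE row | AE/SAE evaluation at Day 90 |
| Protocol 9.4, 9.7 | AE recording and SAE reporting to end of participation |
| SAP 7.1 | No closing day |

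The conflict lies between sections and also inside the schedule, where a tick and the footnote to its column disagree.

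**3. Length of the disputed window**
- Nominal: 90 − 30 = 60 days, and 60/90 = two thirds of follow-up.
- Shortest (Day 30 contact 2 days late, Day 90 contact 7 days early): 83 − 32 = 51 days.
- Longest (Day 30 contact 2 days early, Day 90 contact 7 days late): 97 − 28 = 69 days.

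**4. Which events are affected.** Death is an SAE criterion, and the Day 90 mortality contact finds deaths under either reading. Only non-fatal events are in doubt.

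**5. How much one patient weighs.** With 3:1 allocation in cohorts of 4, 4, 8 and 8, the plan has 3 + 3 + 6 + 6 = 18 patients on CM4620-IE and 1 + 1 + 2 + 2 = 6 on supportive care alone. One more or one fewer patient with an SAE moves the proportion by 1/6 = 16.7 percentage points in the control group, or 1/18 = 5.6 points in the pooled active group. These are the weights of a single patient, not predictions. The documents give no rate of SAEs after Day 30.

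**The case against.** The best case for leaving the text alone is that the mortality-only statements agree with one another and the only contrary scheduling item is one tick. The schedule has no mortality row, so the AE/SAE row is the only one in which a Day 90 contact could be marked, and footnote c then says what that contact is. Section 9.7 can sit beside section 8.10: scheduled questioning to Day 30, plus a duty to report anything learned later. Section 3.2 defines the end of the trial, not of one patient's participation.

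Much of this stands. The tick may well have been meant as a marker for the mortality contact, and placing the end of participation at Day 90 is an inference. But the reader has to construct that reading. Footnote b names SAE evaluation for Day 30 and footnote c does not for Day 90, while the row carries the same tick for both. Even if the tick is a slip, the SAP still has no closing day, so late events that happen to be reported would enter the tables without a rule.

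Three stronger inferences are tempting, and the documents do not support them.
- **Some sites will collect these SAEs and others will not.** All sites could follow section 8.10, or the case report form, which is not among the documents, could settle it.
- **Event counts could triple (90/30 = 3).** That needs a constant SAE rate, which nothing in the documents supports. Section 1.1 describes an early and a late disease phase, deaths are counted either way, and both arms share one schedule.
- **The residual drug levels signal late harm.** Section 1.5 reports one year of follow-up in dosed subjects with no SAEs and no moderate or severe AEs. Those were healthy subjects, so this does not settle the matter for patients, but it is not evidence of harm.

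**Conclusion.** The inconsistency is real and worth correcting. Active ascertainment of non-fatal SAEs is undefined for a nominal 60 of 90 days (51 to 69 with visit windows) and may be inconsistent among patients still alive and in follow-up after Day 30. It matters because safety is the primary objective and, with 6 planned controls, one patient's event is visible in the table. It does not invalidate the trial, and no figure in the plan changes.

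The conclusion rests on reading the schedule row as printed and on inferring from section 3.2 that a patient's participation ends at Day 90. How many events could be missed cannot be estimated from the documents, and neither a difference between sites nor a difference between arms is shown.

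**What to change.** Set one end date for active SAE collection. Bring the synopsis, sections 3.1 and 8.10, schedule footnotes a and c, the AE/SAE row and SAP section 3.2 into line with it and with sections 9.4 and 9.7. State in section 9.4 or 9.7 when an individual's participation ends.

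The preferred version is to ask at Day 90 about SAEs and readmissions since the last contact, because it fits the schedule tick and section 9.7 and uses a contact already planned. Where Day 90 is done by chart review or through the primary physician, the same items should be looked for there. The row label also covers non-serious AEs, so a footnote should say that the Day 90 tick means SAEs only, and section 9.4 should say when recording of non-serious AEs closes. If the sponsor prefers Day 30, removing the tick and stating Day 30 as the end of active collection would also make the documents consistent, at the price of the later window.

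In either case SAP section 7.1 should give the same closing day for the SAE tables and say how events reported after it are shown, for example in listings only.

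The cost is a slightly longer Day 90 contact or chart review, some additional SAE reporting, and wording changes in several places across the two documents.

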## **8.11 Study Assessments**

### **8.11.1 Medical History**

To the extent possible given the patient's medical condition, a complete medical history will be collected at Screening. Demographic data will be collected as the initial part of the medical history. Patients must be specifically questioned for whether they have had previous episodes of acute pancreatitis and whether they have been given a diagnosis of chronic pancreatitis. A family history of either acute or chronic pancreatitis will be obtained. Smoking and alcohol history will be noted as part of the social history. Medications that were being taken prior to enrollment in the study will be collected as part of the medical history as will, if available, baseline laboratories.

### **8.11.2 Concomitant Medications**

Concomitant medications will be recorded from Day 1 through Day 10, or until discharge, whichever comes first. The name, dose and frequency of all medications that the patients are taking will be recorded, including vasopressor(s) and highest dose of vasopressors. Pain medications and anti-pyretic medications, the time of administration of the individual doses, and the route of administration will also be recorded. Generic names should be used when possible.

### **8.11.3 Physical Examination**

A limited physical examination will be performed and recorded at Screening and Day 10, or at discharge if occurring earlier. The physical examination will evaluate the following systems: cardiovascular, respiratory, gastrointestinal, musculoskeletal, and skin. The examination must specifically assess if the patient has abdominal guarding or rebound tenderness.

### **8.11.4 Glasgow Coma Scale Score**

A Glasgow coma scale score will be determined at Day 1 and on Days 2 – 10. If possible, the Glasgow coma scale score should be determined prior to administration of sedatives. Patients should also be free from the effects of paralysis or neuromuscular blocking agents. If the patient

is sedated or paralyzed and the Glasgow coma scale is unable to be performed, please leave blank in the eCRF. The Glasgow coma scale score may be determined using the table below:

**Table 4 Glasgow Coma Scale Score**

	Score
Eye Opening	
Spontaneous	4
Response to verbal command	3
Response to pain	2
No eye opening	1
Best Verbal Response	
Oriented	5
Confused	4
Inappropriate words	3
Incomprehensible sounds	2
No verbal response	1
Best Motor Response	
Obeys commands	6
Localizing response to pain	5
Withdrawal to pain	4
Flexion to pain	3
Extension to pain	2
No motor response	1
Total Score	_____

### 8.11.5 Vital Signs

The recorded vital signs must include the patient’s current temperature, heart rate (beats per minute), systolic and diastolic blood pressures, respiratory rate (breaths per minute), and the total input and output of fluids. The highest and lowest temperatures, the highest heart rate, and the highest respiratory rate since the prior study-required assessment will also be recorded. The total input of fluids (oral and intravenous) and the total output of fluids (urine output and nasogastric output) since the prior study-required assessment will be recorded.

If the patient has been started on vasopressor therapy since the prior study-required assessment, the start time should be recorded. If the patient has been placed on renal replacement therapy since the prior study-required assessment, the type of therapy will be recorded. If the patient has been placed on mechanical ventilation since the prior study-required assessment, the type of ventilation will be recorded (noninvasive or invasive mechanical ventilation). The current settings for fraction of inspired oxygen (FiO2), respiratory rate, tidal volume and positive end-expiratory pressure (PEEP) at the assessment will be recorded. If intra-abdominal pressures are being monitored, the current pressure and the highest pressure since the prior study-required assessment should be recorded. All solid food intake since the prior study-required assessment will be recorded including the time and date of the meal, the percent of the meal completed, if there were nausea or vomiting with the meal, and if pain medications had to be given one hour prior to or after the meal to treat symptoms due to ingesting the meal.

### 8.11.6 Arterial Blood Gas

If an arterial blood gas (ABG) has already been performed as part of supportive care on Days 1, 5 and 10 the pH, PaO2, PaCO2, SaO2 and FiO2 will be recorded.

### 8.11.7 Pulse Oximetry

A pulse oximetry measurement of oxygen saturation, (SpO2), will be measured at Screening and on Days 1 – 10. The PI or appropriately trained study coordinator will review the pulse oximetry waveform to attest to its adequacy. The FiO2 at the time of the pulse oximetry measurement will be recorded. For patients with assisted breathing, the FiO2 is read from the controlled oxygen source e.g. Venturi masks, ventilator and CPAP systems with calibrated oxygen blenders. For patients breathing unassisted i.e. room air, the FiO2 is recorded as 0.21. If a patient is on an uncontrolled oxygen source, the table below allows for the conversion of oxygen flow in L/min to FiO2:

**Table 5 Conversion of O2 Flow to FiO2**

Supplemental Oxygen L/min	Estimated FiO2 (%)		
	Nasal Cannula	Face Mask	Face Mask with Reservoir
Room Air	21		
1	24		
2	28		
3	32		
4	36		
5	40	40	
6	44	50	60
7		50	70
8		60	80
9		60	90
10		60	95

Adapted from EPICII

### 8.11.8 Pregnancy Testing

A serum pregnancy test must be performed for all women of childbearing potential from a blood sample collected at Screening. The result of the test must be negative for the patient to be randomized and receive CM4620-IE.

### **8.11.9 Laboratory Analyses**

At Screening, an amylase or lipase, CBC, differential, and platelets, will be performed at the local lab. The results of the CBC will be used to determine the presence of SIRS. On Days 1 – 5, a CBC, differential, and platelet count will be drawn twice, and chemistry profile will be drawn once, and sent to the central lab. On Days 6 – 10, a CBC, differential, platelet count, and chemistry profile will be collected once and sent to the central lab. The chemistry profile sent to the central lab will consist of sodium, potassium, chloride, bicarbonate, blood urea nitrogen, creatinine, glucose, calcium, total protein, globulin, albumin, alkaline phosphatase, alanine transaminase (ALT), aspartate transaminase (AST), total bilirubin, lactate dehydrogenase (LDH), total cholesterol and triglycerides. The results from these laboratory samples will not be available to the PI or treating physician for the management of the patient with acute pancreatitis.

The PI or treating physician will order all laboratory testing necessary for the management of the patient and analysis will be performed at the local laboratory. Other than at Screening, and all venous and arterial blood gas testing, the blood samples for laboratories ordered as part of the protocol, will be tested at a central lab, and will not be available to assist the PI or treating physician in managing the patient.

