**Table 1 SAD (CM4620-101)**

Group	Active Treatment	Number of Active Treatment Subjects	Number of Placebo Treatment Subjects	IV Dose Volume (mL/kg)
1	0.1 mg/kg	6	2	1.3
2	0.24 mg/kg	3	1	1.3
3	0.48 mg/kg	3	1	1.3
4	1.0 mg/kg	6	2	1.3
5	2.1 mg/kg	6	2	1.3

Of the 32 enrolled subjects, there were no serious adverse events (SAE) or adverse events (AE) classified as moderate or severe in intensity. There were three clinical AEs that were all classified as mild in intensity. Two of the AEs were considered possibly related and one was considered unlikely or unrelated to study treatment. In each case, no action was taken with respect to study treatment because of the AEs. No laboratory abnormalities were observed that were considered clinically significant. There were vehicle-related increases in serum triglyceride and cholesterol levels noted in some subjects that returned to baseline within 24 hours. There was no evidence of any sustained treatment related increase in systolic or diastolic blood pressure. In addition, cardiac function, monitored by continuous electrocardiographic recording and serial biomarker testing, showed no evidence of any treatment related effect on heart rate, QTcF, cardiac troponin-T or B-type natriuretic peptide levels.

In the SAD study (CM4620-101), interim non-compartmental pharmacokinetic (PK) analysis indicates that CM4620 likely distributes to three compartments. Plasma concentrations of compound rise steadily during the 4-hour infusion, with  $T_{max}$  achieved at the end of infusion (4 hours). After the end of infusion, there is a rapid and prominent distribution phase followed by a prolonged period of residual drug levels. The terminal elimination phase has not yet been fully characterized as it appears to be much longer than was anticipated based on pre-clinical PK data in mouse, rat, dog and monkey. Plasma concentrations during the terminal phase are approximately 5% of  $C_{max}$  values and, as indicated above, to date there have been no clinically significant AEs reported during this phase. Plasma exposures, defined by  $AUC_{0-24h}$ , appear to be dose-proportional and reached a maximum of 6710 ng\*h/mL in Group 5, which is 4.3-fold below the mean  $AUC_{24h}$  in monkey at the NOAEL (29,000 ng\*hr/mL).

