**Table 2 MAD (CM4620-102)**

Group	Active Treatment Daily for 7 days	Number of Active Treatment Subjects	Number of Placebo Treatment Subjects	IV Dose Volume (mL/kg)
1	0.5 mg/kg	5	3	0.3125a
2	1.0 mg/kg	6	2	0.625

a one placebo patient received maximum dose volume of 1.3 mL/kg

Subjects in the second group of CM4620-102 were randomized to receive a single dose of active treatment, 1.0 mg/kg, versus placebo for seven consecutive days. Eight healthy subjects were enrolled in the second group, with six receiving active treatment and two receiving placebo for seven consecutive days. There were no SAEs and no AEs classified as moderate or severe in intensity. There were three AEs that were all classified as mild in intensity. In each case, no action was taken with respect to study treatment because of the AEs. No laboratory abnormalities were observed that were considered clinically significant.

There were vehicle-related increases in serum triglyceride noted in some subjects in both groups with levels returning to baseline within 24 hours. Cholesterol levels accumulated in some subjects in both groups with daily dosing but the increases were not considered clinically significant and were related to the vehicle. Thus, the largest rise in cholesterol levels was in the subject who received placebo at the maximum dose volume of emulsion. The rise in cholesterol is believed to be due to the release of tissue cholesterol induced by the lecithin in the emulsion (Byers 1962), was noted in the pre-clinical studies in monkeys, and was reversible with cessation of dosing. There was no evidence of any sustained treatment related increase in systolic or diastolic blood pressure. In addition, cardiac function, monitored by continuous electrocardiographic recording and serial biomarker testing, showed no evidence of any sustained treatment related effect on heart rate, QTcF or B-type natriuretic peptide levels.

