### 8.2 Day 1 (0 hour to < 24 hours)

Perform the following procedures immediately prior to randomization of female patients into Cohort 1 (Cohort 3 during the second phase), and the randomization of male patients into Cohort 2 (Cohort 4 during the second phase):

- Record vital signs

- Record concomitant medications
- Draw a blood sample for CBC, differential and platelets, Chemistry Profile, serum biomarkers—send to central lab
- Obtain a urine sample for biomarker testing—send to central lab
- Record SpO2 and the FiO2 and time performed
- If an ABG has already been performed as part of standard of care, record the pH, PaCO2, PaO2, SaO2 and the FiO2 at the time of draw
- Calculate the Glasgow Coma Scale score
- Record patient's pain using the PNRS
- Assess pain using the CPOT
- **Randomize patient**

If the patient has been randomized to receive CM4620-IE:

- **Start the administration of CM4620-IE (1st dose) as soon as possible after randomization and preferably within 6 hours (up to 8) from the time the patient or legal representative signed the informed consent;**
- If the administration of CM4620-IE is started more than 8 hours from the time the patient or legal representative provided informed consent, note the time and inform the Medical Monitor;
- Draw a blood sample for PK 30 minutes ( $\pm 15$  minutes) after completing the administration of CM4620-IE—send to central lab
- Draw a blood sample for PK 8 hours ( $\pm 30$  minutes) after completing the administration of CM4620-IE—send to central lab

For all patients, at 12 hours ( $\pm 1$  hour) from time of randomization:

- Record vital signs
- Draw a blood sample for CBC, differential and platelets—send to central lab
- Perform an AE/SAE assessment

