### **8.3 Day 2 (24 hours to <48 hours)**

For all patients, at 24 hours ( $\pm 1$  hour) from time of randomization:

- Record vital signs
- Record concomitant medications
- Draw a blood sample for CBC, differential and platelets, chemistry profile, serum biomarkers—send to central lab

- Obtain a urine sample for biomarkers—send to central lab
- Record SpO2 and the FiO2 and time performed
- Calculate the Glasgow Coma Scale Score
- Record patient's pain using the PNRS
- Assess pain using the CPOT
- Perform AE/SAE assessment

For patients randomized to receive CM4620-IE:

- Start the administration of CM4620-IE (**2nd dose**) 24 hours ( $\pm$  1 hour) from the start of dose administration on Day 1
  - Draw a blood sample for PK 30 minutes ( $\pm$ 15 minutes) prior to starting the administration of CM4620-IE—send to central lab

For all patients, at 36 ( $\pm$ 1 hour) hours from the time of randomization:

- Record vital signs
- Draw a blood sample for CBC, differential and platelets—send to central lab

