7.1.2 Analysis

The adverse events will be analyzed using frequencies and percent divided by SOC, and PT code using the TESS approach.

The vital signs will be presented using summary statistics by visit.

Safety laboratory parameters will be presented using shift tables.

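### Scheduled triglycerides are trough values only, so the transient post-infusion rise seen in Phase 1 will probably be understated

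*Protocol*

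**What the plan says.** Protocol 8.11.9 sets the laboratory frequency: "On Days 1 – 5, a CBC, differential, and platelet count will be drawn twice, and chemistry profile will be drawn once". The list of chemistry analytes ends with "lactate dehydrogenase (LDH), total cholesterol and triglycerides", so both lipids are measured once a day.

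Protocol 8.2 takes the first profile immediately before randomization ("Draw a blood sample for CBC, differential and platelets, Chemistry Profile, serum biomarkers—send to central lab"), which makes it the baseline. Protocol 8.3 takes the next one under "For all patients, at 24 hours" from randomization, with a 1-hour window either way ("Draw a blood sample for CBC, differential and platelets, chemistry profile, serum biomarkers—send to central lab"). Protocol 8.4 to 8.6 repeat this at 48, 72 and 96 h. The extra draws at 12, 36, 60 and 84 h are for blood count, differential and platelets only. Protocol 8.11.10 adds draws 30 minutes and 8 hours after the infusion on Days 1 and 4, in CM4620-IE patients, for pharmacokinetics only.

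On the known effect, Protocol 1.5 reports for the single-dose study: "There were vehicle-related increases in serum triglyceride and cholesterol levels noted in some subjects that returned to baseline within 24 hours". For the multiple-dose study it reports: "There were vehicle-related increases in serum triglyceride noted in some subjects in both groups with levels returning to baseline within 24 hours". It also says that cholesterol accumulated in some subjects with daily dosing.

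On analysis, SAP 7.1.2 says "Safety laboratory parameters will be presented using shift tables". SAP 7.1.1 adds absolute and percentage change from baseline, SAP 7 adds summaries by treatment and visit, and SAP 4.5 adds patient listings.

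**The concern.** Phase 1 described a short-lived triglyceride rise caused by the lipid emulsion. The schedule measures triglycerides once per dosing interval, at the point furthest from the infusion, and leaves them out of every draw taken closer to it. A table built on those values can show little movement even if many treated patients have a rise that comes and goes between draws.

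This bears on the primary objective. SAP 3.1.2 names safety laboratory measures among the primary endpoints. Phase 1 subjects were healthy, whereas these patients have acute pancreatitis. The control arm receives no emulsion, so a difference between arms could be seen if the samples were timed to show it. The sponsor's review before Cohorts 3 and 4 would also rest on trough values for this analyte.

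**Working it through.** The plan gives no figure for the interval between infusion and chemistry draw, so there is none to reproduce. Its sample size adds up (4 + 4 + 8 + 8 = 24, of whom 3 + 3 + 6 + 6 = 18 receive CM4620-IE) but matters here only for cost.

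**1. Timing of the draws.** Inputs: infusion over 4 h, every 24 h with a 1-hour window (Protocol 7.4); draws timed from randomization with a 1-hour window (Protocol 8.2 to 8.6). The lag L from randomization to the first dose is not stated. Protocol 8.2 asks for prompt dosing and sets an outer target of 8 h from consent, so I assume L between 0 and 8 h.

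- Chemistry draw: 24 - L - 4 = 20 - L hours after the end of infusion.
- 12-hour-type draw (12, 36, 60, 84 h): 12 - L - 4 = 8 - L hours after the end.

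The tolerance on the chemistry draw is 1 h for dose 1 (draw window) and 2 h for doses 2 to 4 (draw plus dose window).

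| Lag L (h) | Chemistry draw, nominal (h after end) | Dose 1 range | Doses 2-4 range | 12-hour-type draw, nominal |
|---|---|---|---|---|
| 0 | 20 | 19-21 | 18-22 | 8 |
| 2 | 18 | 17-19 | 16-20 | 6 |
| 4 | 16 | 15-17 | 14-18 | 4 |
| 8 | 12 | 11-13 | 10-14 | 0 |

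Protocol 8.11.10 lets the 8-hour pharmacokinetic sample be taken with the 12-hour or 84-hour blood count. That matches a small lag: 4 + 8 = 12 and 72 + 4 + 8 = 84. Whatever the lag, the 12-hour-type draw is nominally 12 h closer to the infusion than the next chemistry draw. The chemistry draw is nominally L hours before the next dose; only with L near 0 and windows at their extremes could it fall up to 2 h into that infusion.

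**2. What the Phase 1 statement bounds.** Return within 24 hours is an upper limit on recovery, and the protocol does not say whether the clock starts at the start or end of infusion. From the start, the nominal draw is at 24 - L hours, at or before the limit. From the end, it is at most 22 h. The statement therefore does not establish that the rise has gone by the draw.

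**3. How much of the rise would be left.** The documents give no decay rate. As an illustration, assume exponential decline from the end of infusion, reaching 5% of the peak rise at time T. The share left at time t is 0.05^(t/T).

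| Assumed T (h after end) | 30 min | 8 h | 12 h | 20 h |
|---|---|---|---|---|
| 24 (24 h after end) | 93.9% | 36.8% | 22.4% | 8.2% |
| 20 (24 h after start) | 92.8% | 30.2% | 16.6% | 5.0% |
| 12 | 88.3% | 13.6% | 5.0% | 0.7% |
| 8 | 82.9% | 5.0% | 1.1% | 0.06% |

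At zero lag, the chemistry draw keeps 8% or less of the peak rise in every row. The 12-hour-type draw keeps 5-37%, and the 30-minute draw 83-94%. At an 8 h lag, the chemistry draw keeps 1-22%.

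**4. Emulsion volume.** At 1.6 mg/mL (Protocol 7.1), volume is dose/1.6: 1.0 gives 0.625, 1.4 gives 0.875, 2.08 gives 1.3 and 1.6 gives 1.0 mL/kg.

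- First phase, 4 days: 0.625 + 3 × 0.875 = 3.25 mL/kg.
- Second phase, 4 days: 2 × 1.3 + 2 × 1.0 = 4.6 mL/kg.
- Multiple-dose group 2 (Protocol Table 2): 4 × 0.625 = 2.5 mL/kg over 4 days, or 7 × 0.625 = 4.375 over its full 7 days.
- Single-dose study: 1.3 mL/kg once in all 32 subjects. Repeated 1.3 mL/kg went to one placebo subject only.

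**The case against.** The strongest reply is that this effect is already described and the daily draws are reasonable. All 32 single-dose subjects received 1.3 mL/kg in one infusion, the largest volume planned here, and the rise was reported as transient. A peak depends mainly on volume per infusion, so the larger cumulative volumes bear more on accumulation, which trough samples can show. Cholesterol accumulation would be seen, and so would slow clearance or carry-over of triglycerides. Investigators may order local tests, and the primary objective also rests on adverse events, vital signs and other laboratory values.

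Most of this stands, and it limits the point. It does not remove it: the earlier subjects were healthy, repeated infusions at 1.3 mL/kg were given to one placebo subject only, and no local triglyceride test is scheduled after an infusion.

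A reader might go further and infer that the protocol's own data show the rise gone by each draw, so that the trial cannot detect it. The documents do not support that. The 24-hour statement is an upper limit with no stated starting point, and the 20-hour interval applies only without a dosing delay. Nor are triglycerides the only known laboratory effect; cholesterol is another.

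**Conclusion.** The schedule yields trough triglycerides only: nominally 20 h after the end of infusion at zero lag and 12 h at an assumed 8 h lag, or 10-22 h across that range with visit windows. No scheduled triglyceride is timed to the transient rise, so the planned tables would probably understate it in these patients. How far depends on an unknown decay rate; the percentages above are illustrations under an assumed exponential decline.

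It would be tempting to add that the trial will report no triglyceride effect. The plan does not say so: the study is descriptive, and the SAP provides change from baseline, summaries by visit and listings as well as shift tables. The gap concerns one transient laboratory measure and leaves the rest of the safety objective intact. It is worth closing because doing so is easy.

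**What to change.** - Add triglycerides to the existing 12-, 36-, 60- and 84-hour draws in both arms (Protocol 8.2 to 8.5, 8.11.9 and Appendix 11).
- In CM4620-IE patients, also add them to the existing 30-minute post-infusion pharmacokinetic draws on Days 1 and 4 (Protocol 8.2, 8.5 and 8.11.10). The 12-hour-type draws alone would miss most of the peak when the lag is small.
- Record the time from the end of infusion for every triglyceride sample in treated patients.
- In SAP 7.1.2, summarise triglycerides by time since infusion and by dose group, with controls shown by time from randomization, alongside the shift table.
- Compare the highest post-baseline value per patient between arms only over draw times common to both. Otherwise the 30-minute samples give the treated arm more chances, nearer the peak, to record a high value.

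Cost: at most 24 × 4 = 96 assays at the 12-hour-type draws plus 18 × 2 = 36 at the 30-minute draws, 132 in all. No new venepuncture is needed, but there is a small added blood volume and central laboratory cost. Dosing and patient care do not change.
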